**Table 5.10-2 Biochemistry from baseline to ASCT – Safety set**

	Baseline N=XX	End of induction N=XX	ASCT N=XX
Biochemistry done			
No	XX (XX.X%)	XX (XX.X%)	XX (XX.X%)
Yes	XX (XX.X%)	XX (XX.X%)	XX (XX.X%)
If yes,			
AST (IU/L)			
N	XX	XX	XX
Missing	XX	XX	XX
Mean (SD)	XX.X (XX.XX)	XX.X (XX.XX)	XX.X (XX.XX)
Median	XX.X	XX.X	XX.X
Q1 ; Q3	XX ; XX	XX ; XX	XX ; XX
Min ; Max	XX ; XX	XX ; XX	XX ; XX
Min ; Max	XX ; XX	XX ; XX	XX ; XX
ALT (IU/L)			
N	XX	XX	XX
Missing	XX	XX	XX
Mean (SD)	XX.X (XX.XX)	XX.X (XX.XX)	XX.X (XX.XX)
Median	XX.X	XX.X	XX.X
Q1 ; Q3	XX ; XX	XX ; XX	XX ; XX
Min ; Max	XX ; XX	XX ; XX	XX ; XX
Min ; Max	XX ; XX	XX ; XX	XX ; XX
Total bilirubin (μmol/L)			
N	XX	XX	XX
Missing	XX	XX	XX
Mean (SD)	XX.X (XX.XX)	XX.X (XX.XX)	XX.X (XX.XX)
Median	XX.X	XX.X	XX.X
Q1 ; Q3	XX ; XX	XX ; XX	XX ; XX
Min ; Max	XX ; XX	XX ; XX	XX ; XX
Min ; Max	XX ; XX	XX ; XX	XX ; XX
Serum creatinine (μmol/L)			
N	XX	XX	XX
Missing	XX	XX	XX
Mean (SD)	XX.X (XX.XX)	XX.X (XX.XX)	XX.X (XX.XX)
Median	XX.X	XX.X	XX.X
Q1 ; Q3	XX ; XX	XX ; XX	XX ; XX
Min ; Max	XX ; XX	XX ; XX	XX ; XX
Min ; Max	XX ; XX	XX ; XX	XX ; XX
Creatinine clearance			
Cockcroft-Gault formula (μmol/L)			
N	XX	XX	XX
Missing	XX	XX	XX
Mean (SD)	XX.X (XX.XX)	XX.X (XX.XX)	XX.X (XX.XX)
Median	XX.X	XX.X	XX.X
Q1 ; Q3	XX ; XX	XX ; XX	XX ; XX
Min ; Max	XX ; XX	XX ; XX	XX ; XX
Min ; Max	XX ; XX	XX ; XX	XX ; XX
MDRD formula (μmol/L)			
N	XX	XX	XX
Missing	XX	XX	XX
Mean (SD)	XX.X (XX.XX)	XX.X (XX.XX)	XX.X (XX.XX)
Median	XX.X	XX.X	XX.X
Q1 ; Q3	XX ; XX	XX ; XX	XX ; XX
Min ; Max	XX ; XX	XX ; XX	XX ; XX
Min ; Max	XX ; XX	XX ; XX	XX ; XX
CKD-EPI formula (μmol/L)			
N	XX	XX	XX
Missing	XX	XX	XX
Mean (SD)	XX.X (XX.XX)	XX.X (XX.XX)	XX.X (XX.XX)
Median	XX.X	XX.X	XX.X
Q1 ; Q3	XX ; XX	XX ; XX	XX ; XX
Min ; Max	XX ; XX	XX ; XX	XX ; XX
Min ; Max	XX ; XX	XX ; XX	XX ; XX

## 5.11 Concomitant treatments

### 5.11.1 Concomitant treatments at inclusion

**Table 5.11-1 Concomitant treatments before baseline\* – Included Set**

		Included Set N=XX
Patients with at least one concomitant treatment		
No		XX (XX.X%)
Yes		XX (XX.X%)
If yes, number of concomitant treatment per patient		
N		XX
Missing		XX
Mean (SD)		XX.X (XX.XX)
Median		XX.X
Q1 ; Q3		XX ; XX
Min ; Max		XX ; XX
Patients with at least one concomitant treatment due to lymphoma		
No		XX (XX.X%)
Yes		XX (XX.X%)

\* Concomitant treatment started before C1D1 and ended before C1D1.

**Listing 5.11-1 Concomitant treatments before baseline\* – Included Set (XX patients)**

Patient identification number	Inclusion date	C1D1	Concomitant treatment					
			Start date	Number	Drug Name (INN)	Indication	End date	Ongoing
XXXXX	XX/XX/XXXX	XX/XX/XXXX	XX/XX/XXXX	XX	XXX	XX	XX/XX/XXXX	X

\* Concomitant treatment started before C1D1 and ended before C1D1.

**Table 5.11-2 Concomitant treatments at baseline\* – Included Set**

			Included Set N=XX
Patients with at least one concomitant treatment			
No			XX (XX.X%)
Yes			XX (XX.X%)
If yes, number of concomitant treatment per patient			
N			XX
Missing			XX
Mean (SD)			XX.X (XX.XX)
Median			XX.X
Q1 ; Q3			XX ; XX
Min ; Max			XX ; XX
Patients with at least one concomitant treatment due to lymphoma			
No			XX (XX.X%)
Yes			XX (XX.X%)

\* Concomitant treatment started before C1D1 and ended during treatment or still on going.

**Listing 5.11-2 Concomitant treatments at baseline\* – Included Set (XX patients)**

Patient identification number	Inclusion date	C1D1	Concomitant treatment					
			Start date	Number	Drug Name (INN)	Indication	End date	Ongoing
XXXXX	XX/XX/XXXX	XX/XX/XXXX	XX/XX/XXXX	XX	XXX	XX	XX/XX/XXXX	X

\* Concomitant treatment started before C1D1 and ended during treatment or still on going.

### 5.11.2 Concomitant treatments during treatment period

**Table 5.112-2 Concomitant treatments during treatment\* – Included Set**

		Included Set N=XX
Patients with at least one concomitant treatment		
No		XX (XX.X%)
Yes		XX (XX.X%)
If yes, number of concomitant treatment per patient		
N		XX
Missing		XX
Mean (SD)		XX.X (XX.XX)
Median		XX.X
Q1 ; Q3		XX ; XX
Min ; Max		XX ; XX
Patients with at least one concomitant treatment due to lymphoma		
No		XX (XX.X%)
Yes		XX (XX.X%)

\* Concomitant treatment started after C1D1 or with missing starting dates but still on going.

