10.4 Concomitant treatment

Any patient treatments taken 8 days prior to study treatment, at any time during the study and up to 28 days after the end of the study treatment will be considered as concomitant treatments.

10.4.1 **Prohibited therapies**

The following concomitant treatments are not permitted during this study treatment:

- Systemic anticancer agents other than study drugs.
- Other investigational therapies or devices.
- Concomitant radiotherapy.

If a patient's clinical status requires administration of a prohibited concomitant medication or treatment, then administration of study drugs should be stopped, and the patient will be withdrawn from the study treatment.

The change in clinical status mandating the use of the medication in question must be reported as the reason for study drug discontinuation.

10.4.2 **Restricted/allowed therapies**

Patients will be instructed not to take any additional medications (including over-the-counter products) during the course of the study without prior consultation with the investigator. At each visit, the investigator will ask the patient about any new medications he/she is or has taken after the start of the study drug.

All therapies necessary for the patient management are permitted besides other antineoplastic agents for lymphoma. The use of antibiotics and other supportive therapies is in the discretion of the treating physician.

Administration of Granulocyte colony-stimulating factor is mandatory after each GA101-DHAP cycle and recommended after autologous stem cell transplant (see section 10.2).

Platelet and red blood cell transfusions are permitted, as necessary.

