10.5 Prophylactic measures

10.5.1 **Infusion-Related Reactions related to Obinutuzumab**

The most frequently observed adverse drug reactions (ADR) in patients receiving Obinuzumab were IRR; these occurred predominantly during the first infusion. The incidence and severity of infusion related symptoms decreased substantially with subsequent infusion.

See also section 10.1.5. *Administration* for the management of IRR

During induction treatment, dexamethasone should be administrated before the infusion of Obinutuzumab

If a patient experiences an IRR during the prior infusion, he should receive 100mg prednisolone or equivalent.

If a patient does not experience an IRR (grade ≥ 1) during the first infusion, the premedication for the infusions of maintenance can be omitted.

The first Obinutuzumab infusion should be administered to patient after premedication with oral analgesic/anti pyretic (e.g. 1000mg) and anti-histaminic drug (e.g. 50 mg diphenhydramine)

Grade 4 (life-threatening)	Stop infusion and discontinue therapy.
Grade 3 (severe)	Temporarily interrupt infusion and treat symptoms. Upon resolution of symptoms, restart infusion at no more than half the previous rate (the rate being used at the time that the IRR occurred) and, if patient does not experience any IRR symptoms, infusion rate escalation may resume at the increments and intervals as appropriate for the treatment dose
Grade 1-2 (mild and moderate)	Reduce infusion rate and treat symptoms. Upon resolution of symptoms, continue infusion and, if patient does not experience any IRR symptoms, infusion rate escalation may resume at the increments and intervals as appropriate for the treatment dose

10.5.2 ***Tumor Lysis Syndrome***

Patients who are considered to be a risk of TLS (e.g. patients with a high tumor burden or a high circulating lymphocyte count) should receive adequate tumor lysis prophylaxis with allopurinol (or adequate alternative) and hydration starting 12-24 hours prior to the infusion of Obinutuzumab.

10.5.3 ***Infection***

Obinutuzumab should not be administrated in the presence of an active infection.

Prophylaxis of infections is required for all patients during all the study treatment, in the discretion of the treating physician.

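### The SAP 5.11 date rules leave drugs started on C1D1, and two other kinds of record, out of every concomitant-treatment table and listing

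*SAP*

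**What the plan says.** SAP 5.11 has three pairs of a table and a listing, each with a footnote that states its date rule:

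- Table and Listing 5.11-1 (before baseline): "Concomitant treatment started before C1D1 and ended before C1D1".
- Table and Listing 5.11-2 (at baseline): "Concomitant treatment started before C1D1 and ended during treatment or still on going".
- Table and Listing 5.112-2, in the section headed "Concomitant treatments during treatment period": "Concomitant treatment started after C1D1 or with missing starting dates but still on going".

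SAP 4.6 rules out imputing missing values.

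Protocol 10.4 sets the window within which a drug counts as concomitant. It opens with "Any patient treatments taken 8 days prior to study treatment, at any time during the study" and closes with "up to 28 days after the end of the study treatment will be considered as concomitant treatments". SAP 5.11 neither restates nor cites this window.

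Protocol 10.2.1.1 places the first obinutuzumab infusion on C1D1 with standard premedication. Protocol 10.5.1 says: "The first Obinutuzumab infusion should be administered to patient after premedication with oral analgesic/anti pyretic", and adds an antihistamine. Protocol 10.5.3 requires infection prophylaxis for all patients throughout study treatment.

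**The concern.** The footnotes are explicit date rules, and a programmer who follows them must leave out any record that meets none of them. C1D1 is a day on which the protocol expects new drugs to start, so the missing boundary is not a remote case. If such drugs are entered as concomitant treatment, the per-patient counts for the treatment period come out too low and the listing omits drugs that were given.

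The third rule also has no closing date, so the SAP alone does not tell the programmer to apply the protocol's 28-day limit. The SAP's introduction gives pre-specification before database lock as its purpose. On this point it leaves the programmer to choose between strictly after and on or after, and to decide whether the limit applies.

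**Working it through.** The plan states no figure here to reproduce, so the check is a classification of test records.

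**Inputs.** Day 0 = C1D1. Day T = end of study treatment; T = 2300 was used as an arbitrary value and does not affect the result. s = start day and e = end day. Ongoing means no end date, in line with the separate end-date and ongoing columns in the SAP listings.

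**Rules as written.**

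- 5.11-1: s < 0 and e < 0.
- 5.11-2: s < 0 and (0 ≤ e ≤ T or ongoing).
- 5.112-2: s > 0, or s missing and ongoing.

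**Rules after the change set out under the fix.**

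- 5.11-1: (s < 0 or s missing) and e < 0.
- 5.11-2: s < 0 and (e ≥ 0 or ongoing).
- 5.112-2: 0 ≤ s ≤ T + 28, or s missing and not known to have ended before day 0. Here T is taken as the day of the last administration.

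| Record | As written | After the change |
|---|---|---|
| s = −5, e = −1 | 5.11-1 | 5.11-1 |
| s = −5, e = 0 | 5.11-2 | 5.11-2 |
| s = −5, ongoing | 5.11-2 | 5.11-2 |
| s = −5, e = T + 10 | none | 5.11-2 |
| s = 0, e = 0 | none | 5.112-2 |
| s = 0, e = 10 | none | 5.112-2 |
| s = 0, ongoing | none | 5.112-2 |
| s = 1, e = 5 | 5.112-2 | 5.112-2 |
| s = T + 28 | 5.112-2 | 5.112-2 |
| s = T + 365 | 5.112-2 by the footnote alone; outside protocol 10.4 | none, by design |
| s missing, ongoing | 5.112-2 | 5.112-2 |
| s missing, e = 30 | none | 5.112-2 |
| s missing, e = −1 | none by the letter, though the start must precede day 0 | 5.11-1 |

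**Reading the table.** Every record with s = 0 is lost, whatever its end date. A missing start with a known end is lost because the third rule accepts a missing start only when the drug is ongoing, and SAP 4.6 allows no imputed date. A start before C1D1 with an end after treatment is lost because the second rule accepts only an end during treatment or an ongoing drug. Changing strictly after to on or after and adding the 28-day limit would cure the first loss only; the other two need their own wording.

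**Size.** Protocol 10.5.1 names two kinds of premedication for the first infusion besides dexamethasone, which belongs to the induction regimen. If both are entered as concomitant treatments starting on C1D1, about 2 records per treated patient are lost. If premedication is not entered that way, 0 are lost. Other C1D1 starts add to either figure.

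**The case against.** The strongest reply is that a programmer would read after C1D1 as on or after, and that little depends on the result. The tables have only an any/none row, a number per patient and a lymphoma-related row, with no rows by drug or class. No planned analysis relates these drugs to infusion reactions or tumour lysis. That stands as a limit on importance. It does not remove the gap, because the SAP nowhere says on or after, and the listings do name individual drugs.

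A reader might also infer that the open-ended third rule fills the treatment-period table with drugs started years later in follow-up. The documents do not support that:

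- Protocol 10.4 already stops counting a drug as concomitant 28 days after study treatment.
- The follow-up assessments in protocol 9.10.1 list no medication item, and after progression 9.10.2 records only survival status and other malignancies.
- The 6.5 years after last inclusion in protocol section 7 is mostly the planned treatment period: 12/52 + 3 + 3 ≈ 6.2 years before the transplant phase is added. Drugs started years after C1D1 can therefore belong in the table.

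What remains of that reading is narrower. The SAP should state the limit, because the words in 10.4 about any time during the study are loose.

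Nor is tumour-lysis prophylaxis generally lost. Protocol 10.5.2 starts it 12 to 24 hours before the infusion, so it will usually have a start date before C1D1 and meet one of the first two rules.

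**Conclusion.** The point holds and is minor. Applied as written, the three footnotes do not cover all concomitant treatments: a C1D1 start, a missing start with a known end, and an early start with an end after treatment each enter no table or listing. The missing 28-day limit is an omission from the SAP, not evidence of an over-count.

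It is tempting to put a firm count on the loss, such as 2 × 70 = 140 records, or 2 × 83 = 166. The documents do not support either as a minimum. Both assume that each premedication drug is a separate eCRF record dated C1D1, which the documents do not describe. The figure of 83 also allows for included patients who are never treated. The supportable range is 0 to about 2 premedication drugs per treated patient, plus an unknown number of other C1D1 starts and of the two other record types.

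The conclusion assumes that the footnotes are applied literally and that ongoing means no end date. It touches only the descriptive concomitant-treatment tables and listings. The primary endpoint, the decision rule and the adverse-event rates are unaffected.

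**What to change.** - **Table and Listing 5.112-2:** replace the footnote with *started on or after C1D1 and no later than 28 days after the last study treatment administration, or start date missing and not known to have ended before C1D1*.
- **Tables and Listings 5.11-1 and 5.11-2:** keep *started before C1D1* and split on the end date. Drugs that ended before C1D1 go to 5.11-1; drugs that ended on or after C1D1, or are ongoing, go to 5.11-2. A missing start date with an end before C1D1 goes to 5.11-1.
- **Drugs started after the 28-day window:** leave them out of these tables, since protocol 10.4 does not count them as concomitant. They should not be rerouted wholesale to the outputs in SAP 5.8 and 5.12, which hold anticancer therapy only; only such therapy belongs there.

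The sponsor should confirm that the last administration is the intended end of study treatment for patients who pass through the on-demand phase without receiving drug.

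The cost is a few lines of footnote text and the matching date comparisons in the program. No new data are needed.

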**Listing 5.112-2 Concomitant treatments during treatment\* – Included Set (XX patients)**

Patient identification number	Inclusion date	C1D1	Concomitant treatment					
			Start date	Number	Drug Name (INN)	Indication	End date	Ongoing
XXXXX	XX/XX/XXXX	XX/XX/XXXX	XX/XX/XXXX	XX	XXX	XX	XX/XX/XXXX	X

\* Concomitant treatment started after C1D1 or with missing starting dates but still on going.

### 5.12 Non study treatments out of progression

**Table 5.122-1 Non study treatment treatment out of progression – Safety Set**

		Safety Set N=XX
Non study treatment out of progression		
No		XX (XX.X%)
Yes		XX (XX.X%)
If yes, Monoclonal antibody		
No		XX (XX.X%)
Yes		XX (XX.X%)
If yes, Other immunotherapy		
No		XX (XX.X%)
Yes		XX (XX.X%)
If yes, Chemotherapy		
No		XX (XX.X%)
Yes		XX (XX.X%)
If yes, Radiotherapy		
No		XX (XX.X%)
Yes		XX (XX.X%)
If yes, Autologous transplant		
No		XX (XX.X%)
Yes		XX (XX.X%)
If yes, Allogenic transplant		
No		XX (XX.X%)
Yes		XX (XX.X%)
If yes, IMiD		
No		XX (XX.X%)
Yes		XX (XX.X%)
If yes, Epigenetic modifiers agents		
No		XX (XX.X%)
Yes		XX (XX.X%)
If yes, Kinase inhibitors		
No		XX (XX.X%)
Yes		XX (XX.X%)
If yes, Other anti-cancer therapy		
No		XX (XX.X%)
Yes		XX (XX.X%)

**Listing 5.122-1 Patients who received monoclonal antibody as non study treatment treatment out of progression – Safety Set (XX patients)**

Patient identification number	Inclusion date	Permanent treatment discontinuation		Non study treatment treatment out of progression		
		Date	Reason	Monoclonal antibody	Date	Drug name
XXXXX	XX/XX/XXXX	XX/XX/XXXX	XX	Yes	XX/XX/XXXX	XXX

**Listing 5.122-2 Patients who received other immunotherapy as non study treatment treatment out of progression – Safety Set (XX patients)**

Patient identification number	Inclusion date	Permanent treatment discontinuation		Non study treatment treatment out of progression		
		Date	Reason	Other immunotherapy	Date	Drug name
XXXXX	XX/XX/XXXX	XX/XX/XXXX	XX	Yes	XX/XX/XXXX	XXX

**Listing 5.122-3 Patients who received chemotherapy as non study treatment treatment out of progression – Safety Set (XX patients)**

Patient identification number	Inclusion date	Permanent treatment discontinuation		Non study treatment treatment out of progression		
		Date	Reason	Chemotherapy	Date	Drug name
XXXXX	XX/XX/XXXX	XX/XX/XXXX	XX	Yes	XX/XX/XXXX	XXX

**Listing 5.122-4 Patients who received autologous transplant as non study treatment treatment out of progression – Safety Set (XX patients)**

Patient identification number	Inclusion date	Permanent treatment discontinuation		Non study treatment treatment out of progression			
		Date	Reason	Autologous transplant	Date of transplant	Type of autologous transplant intensive chemotherapy with HSCT	Date of autologous transplant intensive chemotherapy
XXXXX	XX/XX/XXXX	XX/XX/XXXX	XX	Yes	XX/XX/XXXX	XXX	XX/XX/XXXX

**Listing 5.122-5 Patients who received allogenic transplant as non study treatment treatment out of progression – Safety Set (XX patients)**

Patient identification number	Inclusion date	Permanent treatment discontinuation		Non study treatment treatment out of progression			
		Date	Reason	Allogenic transplant	Date of transplant	Type of allogenic transplant intensive chemotherapy with HSCT	Date of allogenic transplant intensive chemotherapy
XXXXX	XX/XX/XXXX	XX/XX/XXXX	XX	Yes	XX/XX/XXXX	XXX	XX/XX/XXXX

**Same listing for (no listing if empty) :**

- Kinase
- ImiD
- ...

## 7 APPENDICES

### 7.1 Demographic and other baseline characteristics

**Table 5.12-1 Clinical examination at baseline - Included Set**

		Included Set N=XX
Clinical examination at baseline		
Normal		XX (XX.X%)
Abnormal		XX (XX.X%)
Not done		XX (XX.X%)
If Abnormal, specify		
Due to active lymphoma		XX (XX.X%)
XXXXX		XX (XX.X%)
Due to study treatment		XX (XX.X%)
XXXXX		XX (XX.X%)
Due to other reason		XX (XX.X%)
XXXXX		XX (XX.X%)

**Listing 5.12-1 Patients with abnormal electrocardiogram at baseline – Included Set (XX patients)**

Patient identification number	Inclusion date	Electrocardiogram		
		Date	Result	If abnormal, specify
XXXXX	XX/XX/XX	XX/XX/XX	Abnormal	XXXXX

**Listing 5.12-2 Patients with other important exams performed at baseline – Included Set (XX patients)**

Patient identification number	Inclusion date	Other important exams		
		Number	Description	Date
XXXXX	XX/XX/XX	1	XXXXX	XX/XX/XX
		2	XXXXX	XX/XX/XX

**Table 5.12-2 Prior cancer history at baseline – Included Set**

		Included Set N=XX
Patients with prior cancer history		
No		XX (XX.X%)
Yes		XX (XX.X%)
If yes, number of cancer per patient		
N		XX
Missing		XX
Mean (SD)		XX.X (XX.XX)
Median		XX.X
Q1 ; Q3		XX ; XX
Min ; Max		XX ; XX

**Listing 5.12-3 Prior cancer history at baseline – Included Set (XX patients)**

Patient identification number	Inclusion date	Prior cancer history			
		Number	Type of prior cancer	Start date	End date
XXXXX	XX/XX/XX	XX	XXXXX	XX/XXXX	XX/XXXX

**Table 5.12-3 Relevant medical history at baseline – Included Set**

		Included Set N=XX
Patients with relevant medical history		
No		XX (XX.X%)
Yes		XX (XX.X%)
If yes, number of disease per patient		
N		XX
Missing		XX
Mean (SD)		XX.X (XX.XX)
Median		XX.X
Q1 ; Q3		XX ; XX
Min ; Max		XX ; XX

**Listing 5.12-4 Relevant medical history at baseline – Included Set (XX patients)**

Patient identification number	Inclusion date	Relevant medical history			
		Number	Type of disease	Start date	Persisting
XXXXX	XX/XX/XX	XX	XXXXX	XX/XXXX	XX

**Table 5.12-4 Serology at baseline – Included Set**

	Included Set N=XX
HIV serology	
Negative	XX (XX.X%)
Positive	XX (XX.X%)
Not Done	XX (XX.X%)
HCV serology	
Negative	XX (XX.X%)
Positive	XX (XX.X%)
Not Done	XX (XX.X%)
HBV serology (HBs Ag)	
Negative	XX (XX.X%)
Positive	XX (XX.X%)
Not Done	XX (XX.X%)
HBV serology (anti HBs)	
Negative	XX (XX.X%)
Positive	XX (XX.X%)
Not Done	XX (XX.X%)
HBV serology (anti HBc)	
Negative	XX (XX.X%)
Positive	XX (XX.X%)
Not Done	XX (XX.X%)
HBV vaccination	
No	XX (XX.X%)
Yes	XX (XX.X%)
Unknown	XX (XX.X%)
Result of PCR for viral DNA of BV	
Negative	XX (XX.X%)
Positive	XX (XX.X%)
Not Done	XX (XX.X%)

**Table 5.12-5 Female childbearing status - Included Set**

	Included Set N=XX
Is female of childbearing potential	
No	XX (XX.X%)
Yes	XX (XX.X%)
If yes, result of pregnancy test	
Negative	XX (XX.X%)
Positive	XX (XX.X%)
Not Done	XX (XX.X%)

## 7.2 Evaluation during study

**Listing 5.12-1 Patients with abnormal clinical exam during treatment – Safety Set (XX patients)**

Patient identification number	Inclusion date	Clinical exam						
		Period	Date	Result	Due to Lymphoma	Due to study treatment	Due to other reason(s)	Specify
XXXXX	XX/XX/XX	XX	XX/XX/XXXX	Abnormal	XX	XX	XX	XX

## 7.3 Appendix A: Calculation of total dose and PPD

Percentage of Planned Dose is defined as follow:

$$PPD = \frac{\text{Total dose taken in mg/m}^2}{\text{Total dose expected in mg/m}^2} \times 100$$

**Table 7.6-1 Calculation of total dose taken and expected**

	Total dose taken	Total dose expected
Cycle i	Sum of doses administered during Cycle i	Sum of doses expected during Cycle i
Cycle i - Cycle j	Sum of doses administered from Cycle i to Cycle j	Sum of doses expected from Cycle i to Cycle j when administered

**Table 7.6-2 Expected dose for cycle 1 according to the protocol**

Chemotherapy regimen	Dose	D1	D2	D3	D4	D8	D15
Dexamethasone	40mg	X	X	X	X		
GA-101 IV	1000mg	X				X	X
Aracytine IV (every 12 hours)	2 g/m 	X X					
Cisplatin* IV	100 mg/m 	X					

**Table 7.6-3 Expected dose for cycle 2 to 4 according to the protocol**

Chemotherapy regimen	Dose	D1	D2	D3	D4
Dexamethasone	40mg	X	X	X	X
GA-101 IV	1000mg	X			
Aracytine IV (every 12 hours)	2 g/m 	X X			
Cisplatin* IV	100 mg/m 	X			

